4.3.3. Primary HRQoL Analysis

The primary HRQoL analysis is defined prospectively as a comparison of the longitudinal change in TOI scores for significant between-group difference using linear mixed models. The models will include baseline variables (baseline TOI score, and possibly other baseline variables predictive of TOI outcome) as covariates and treatment arm and time (and their interaction) as fixed effects. Time will include the baseline, 12 week, 18 week and 24 week time-points.

These models account for covariance between repeated measures on participants and will be used to: i) describe the time course of the TOI over time; ii) assess whether the time course differs between the two treatment arms by testing the study arm-by-time interaction; and iii) estimate and test differences between the two treatment arms at specific time points of interest via selected linear contrasts. Sensitivity analyses will be performed using pattern-mixture models and/or joint model of longitudinal and survival data to help interpret results if greater than 20% of the TOI data are missing, and if reasons for missing data (from the CoMiDa form) and patterns of missing data (described in **Section 4.3.2.**) suggest that these when data are not missing at random.

4.3.3.1. Subgroup Analysis for the Primary Efficacy Endpoint

In addition to the analysis of the overall study population, pre-specified subgroup analysis will be conducted for the TOI (primary efficacy endpoint) using linear mixed models to detect significant differences in longitudinal change in TOI score between treatment groups in the following subgroups: i) palliative-intent treatment subgroup; and ii) adjuvant/curative-intent treatment subgroup.

4.3.4. Secondary HRQoL Analyses

Secondary HRQoL analyses, defined prospectively, includes: i) comparison of the proportions of participants in the two treatment arms with at least 10 units deterioration in TOI score at 12 weeks and 24 weeks by using Fisher's exact test (as recommended by NCIC CTG)(72); and ii) time to deterioration in TOI score (defined as the time from randomisation to a minimum 10 units deterioration in change score from baseline) by log-rank test.

4.3.5. Tertiary HRQoL Analyses

Tertiary HRQoL analyses will be performed on all scales of the EORTC QLQ-C30, QLQ-ELD14 and EQ-5D-5L to complement primary and secondary HRQoL analyses, to make full use of all HRQoL data collected, and to assist in interpretation of the primary endpoint. The t-test or Wilcoxon test will be applied, depending on normality of distribution, to each of the scales of the QLQ-C30 and QLQ-ELD14 (using the EORTC's standard scoring algorithms) and the EQ-5D-5L, to assess between-group differences in change from baseline to 12 weeks and 24 weeks, across a comprehensive range of HRQoL domains. The TOI will also be analysed in this way for completeness.

4.3.6. Adjustment for Multiple Hypothesis Testing

For the primary HRQoL analysis, adjustment for multiple comparisons of TOI differences at specific times will be undertaken using the Hochberg method.(74) No formal adjustment will be used for other secondary or exploratory analyses. In general, two-sided P-values will be used and 95% confidence limits for all important endpoints will be reported.

4.4. Secondary Efficacy Analyses

4.4.1. Overall Survival

Overall survival between treatment groups will be analysed using a closed hierarchical method in the following pre-specified order: (1) palliative-intent treatment subgroup; (2) overall study population; and (3) adjuvant/curative-intent treatment subgroup.

Overall survival will be estimated using the non-parametric Kaplan-Meier method. Summary statistics will be presented with appropriate confidence intervals. The non-parametric log rank test will be used to compare the two arms of the study and, if appropriate, a Cox proportional hazard model will be used to estimate the treatment effects. Additional details will be provided in the SAP.

4.4.2. Other Secondary Endpoints

Other secondary endpoints will be summarised according to established guidelines specific to the measurement instrument. In general, categorical variables will be tabulated and key summary statistics (mean, standard deviation, median, range, etc.) will be presented for continuous measurements. Comparisons between treatment arms will be made where appropriate and the test selected depending on the distribution. Additional details will be provided in the SAP.

4.5. Exploratory Analyses

4.5.1. Economic Evaluation

An exploratory economic evaluation will be performed comparing the healthcare costs and benefits of integrated geriatric care compared to standard oncology care from randomisation to 24 weeks post-randomisation. Data on outcomes will be collected on study participants including health utilities through the EQ-5D-5L and costs will be calculated for the use of healthcare resources such as Medicare-reimbursed costs, medications (including chemotherapy), emergency department visits, hospital stays and the use of other healthcare services (including allied health, rehabilitation, aged care and palliative care).

Health economic data will be assessed using descriptive statistics. Healthcare utilisation will be valued using standard hospital and/or Medicare prices to obtain total cost per participant. The Incremental Cost-Effectiveness Ratio (ICER) will be calculated as the cost per adjusted quality adjusted survival (cost/QALY gain), using the EQ-5D-5L utility scores. The robustness and validity of these results will be tested using sensitivity analyses.

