3.1. Overview

All analyses will be conducted as defined in a formal statistical analysis plan (SAP) for the analysis and presentation of data. The SAP will be finalised prior to commencement of study analysis and approved by the Trial Management Committee (TMC).

This document constitutes the formal statistical analysis plan (SAP).

All analyses will be conducted according to the intention-to-treat (ITT) principle: all eligible and evaluable participants will be included in the analysis and analysed according to the arm randomised to (using the as-randomised participant population). By using the ITT principle, the benefits of randomisation are maintained (i.e. that the trial arms are similar except for intervention).

Baseline characteristics by treatment arm will be summarised in frequency tables and by use of descriptive statistics for quantitative variables. Univariate associations will be identified using independent T-test for comparing means, χ^2 or Fisher's exact test for comparing categorical data. Confounder bias will be minimised with logistic regression by adjusting for age plus other relevant differences between the groups (comorbidity, metastatic disease, chemotherapy dose reduction at the outset) in bivariate and multivariate analysis.

Summary tables will be prepared giving numbers of participants by treatment arm and by randomisation irregularities, treatment compliance, eligibility infringements, and losses to follow-up (as per CONSORT guidelines).(19)

Table 1. Baseline characteristics by treatment group

Characteristic	Intervention	Usual Care
Age		
Mean		
Median		
Range		
Sex		
Male		
Female		
Marital status		
Married		
Separated, divorced		
Widowed		
Single		
Household composition		
Lives in the community with spouse, partner or child		
Lives in the community alone		
Lives in residential care		
Cancer site		
Upper gastrointestinal		
Lower gastrointestinal		
Lung		
Urogenital		
Breast		
DLBCL		
Other, not specified		
Cancer stage		
II		
III		
IV		

Treatment intent		
Curative/neoadjuvant/adjuvant		
Palliative		
Initial anti-cancer treatment		
Cytotoxic chemotherapy		
Immunotherapy		
Targeted therapy		
Treatment line		
1 st line		
2 nd line		
3 rd line and beyond		
Patient-reported outcomes		
ELFI score		
EQ-5D-5L utility score		
ECOG 0-1		
KPS \geq 80		
IADL unimpaired		
ECOG 0-1		
KPS \geq 80		
PHQ-9		
GAD-7		

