- Institutionalisation A secondary endpoint of this study is the hazard ratio of institutionalisation of participants in the two treatment arms; this will be compared between treatment arms. In addition, the level of care level of care and social situation will also be described in the treatment arms.

The following endpoint definition was changed from the protocol:

- Chemotherapy delivery: the proportion of participants with dose delays in the two treatment arms at 12 weeks and 24 weeks. Dose delay is defined as a delay of more than 3 days in the start of chemotherapy measured since the start of the previous cycle.

The following endpoints were not defined in the protocol, but will be analysed as exploratory endpoints to supplement the pre-specified secondary endpoints:

- QLU-C10D health utility
- QLU-C10D health utility score in the two treatment arms at 12 weeks and 24 weeks will be compared between treatment arms.(27, 28)
- The QLU-C10D health utility scores will also be used in the health economic analysis, in place of the EQ-5D-5L scores, to determine if the same or different conclusions would be reached with either utility measure.
- Chemotherapy delivery
- Primary dose reduction (PDR) will be compared within treatment arms. PDR is defined as dose of chemotherapy which is less than the dose recommended for given regimen in current treatment guidelines by NCCN (excluding round-off).
- Mean % dose reduction at outset will be compared within treatment arms.
- Median % dose reduction at outset will be compared within treatment arms.
- Early discontinuation of chemotherapy will be compared within treatment arms.
- Mean cycles of chemotherapy delivered will be compared within treatment arms.
- Median cycles of chemotherapy delivered will be compared within treatment arms.

Table 4. Summary of secondary and additional exploratory endpoints, data type, data timepoints and statistical tests are listed in the table below.

Endpoints	Data Type	Data output	Data Timepoints	Statistical Tests
Function				
ECOG-PS	Categorical ordinal (0,1,2,3,4)	contingency table	Baseline Wk12 Wk24	contingency table analysis
KPS	Categorical ordinal (30,40,50,60,70,80,90,100)	contingency table	Baseline Wk12 Wk24	contingency table analysis
Katz ADL scale	6-item, categorical dichotomous scale (i) → dichotomous outcome (unimpaired, impaired) (ii) → dichotomous outcome (any decrease in ADL)	1. unimpaired vs impaired 2. decrease in ADL	Baseline Wk12 Wk24	contingency table analysis

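### The exploratory cost-utility analysis states no adjustment for the baseline utility already collected, so chance baseline imbalance enters the QALY difference and precision is given up

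*Combined protocol and SAP*

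**What the plan says.** Protocol 4.5.1 sets the horizon of the economic evaluation as "from randomisation to 24 weeks post-randomisation" and labels it exploratory. On method it says "Health economic data will be assessed using descriptive statistics", defines the ICER in the sentence "The Incremental Cost-Effectiveness Ratio (ICER) will be calculated as the cost per adjusted quality adjusted survival (cost/QALY gain), using the EQ-5D-5L utility scores", and closes with "The robustness and validity of these results will be tested using sensitivity analyses". It does not say how a QALY is computed, how deaths are scored, or what the sensitivity analyses contain.

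The SAP has no economic section. SAP 3.5.2 adds one element: "The QLU-C10D health utility scores will also be used in the health economic analysis, in place of the EQ-5D-5L scores".

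The forms schedules (protocol 3.6.1, SAP 2.5.1) place EQ-5D-5L at baseline and weeks 12, 18 and 24. SAP Table 1 lists "EQ-5D-5L utility score" as a baseline characteristic. The QLQ-C30, from which QLU-C10D is derived, is scheduled at baseline and weeks 12 and 24 only.

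For the primary endpoint the plan does adjust for baseline. Protocol 4.3.3 states: "The models will include baseline variables (baseline TOI score, and possibly other baseline variables predictive of TOI outcome) as covariates". SAP 3.4.3 repeats this for the renamed index.

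**The concern.** A QALY counted from randomisation is an area under the utility curve, and that curve starts at the baseline value. If one arm starts higher by chance, its QALYs are higher for two reasons: the starting value is part of the area, and later utilities are correlated with it. A plain difference in mean QALYs passes this into the ICER denominator.

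Nothing else in the documents deals with it:

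- The word *adjusted* in the ICER sentence is tied to no covariate or model.
- SAP 3.1 describes confounder adjustment by logistic regression on age, comorbidity, metastatic disease and initial dose reduction. Baseline utility is not listed, and logistic regression does not suit a QALY.
- Minimisation (protocol 3.4.1) uses treatment intent, tumour type, age, gender and physician-rated ECOG, not utility.

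The SAP's question of whether the two utility instruments lead to the same conclusion is exposed as well. Each instrument can have its own baseline imbalance, so a disagreement might partly reflect chance at baseline.

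**Working it through.** **The plan's own figure.** Protocol 4.2 uses a two-sided 0.05 test, 80% power and an effect of 0.5 SD. The normal approximation gives n = 2(1.960 + 0.842)²/0.5² = 62.8, so 63 per arm. The t-based calculation gives 63.8, so 64 per arm. The stated 64 reproduces. It was set for the primary index; the plan gives no figure for the economic evaluation.

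**Assumptions not in the plan.** Trapezium rule; equal utility SD at each visit, taken as 0.2; the same correlation ρ between any two visits, 0.3 to 0.7; complete data; 64 per arm.

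**Weights.** For visits at 0, 12, 18 and 24 weeks the trapezium weights are 6, 9, 6 and 3 weeks (sum 24), each divided by 52. Their squares sum to 36 + 81 + 36 + 9 = 162, and 24² = 576.

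**Formulas, per unit SD, in weeks.**

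- Var(area) = 162 + ρ(576 − 162)
- Cov(area, baseline) = 6 + 18ρ
- R² = Cov²/Var; SE ratio, adjusted to raw = √(1 − R²)
- QALY shift per unit of baseline difference = Cov/52

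| ρ | Var | Cov | R² | SE ratio | SE cut | Shift per unit | Shift at gap 0.05 |
|---|---|---|---|---|---|---|---|
| 0.3 | 286.2 | 11.4 | 0.45 | 0.74 | 26% | 0.219 | 0.011 |
| 0.5 | 369.0 | 15.0 | 0.61 | 0.63 | 38% | 0.288 | 0.014 |
| 0.7 | 451.8 | 18.6 | 0.77 | 0.48 | 52% | 0.358 | 0.018 |

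The SE of the baseline difference is 0.2 × √(2/64) = 0.035, so a gap of 0.05 is 1.4 SE. At ρ = 0.5 the SE of the QALY difference falls from 0.0131 to 0.0082.

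**With deaths.** Simulations at ρ = 0.5 assumed mean utility 0.75, SD 0.2 and zero utility after death, with the hazard either independent of baseline utility or rising as it falls.

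| Dead by week 24 | R² | SE cut |
|---|---|---|
| none | 0.61 | 38% |
| about 10% | 0.35 to 0.43 | 19% to 24% |
| about 20% | 0.24 to 0.36 | 13% to 20% |

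Across the death scenarios the shift per unit of baseline difference stays at 0.26 to 0.35. Deaths reduce the precision gain but leave the carry-over largely as it was.

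**QLU-C10D.** Without week 18 the weights are 6, 12 and 6. Then Var = 216 + 360ρ and Cov is again 6 + 18ρ. R² is 0.40, 0.57 and 0.74 for ρ = 0.3, 0.5 and 0.7, so the conclusion is the same with slightly smaller gains.

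**Change from baseline is not a substitute.** Subtracting baseline over the whole period changes the weights to −18, 9, 6 and 3, with variance 450(1 − ρ). At ρ = 0.3 that is 315 against 286.2, a ratio of 1.10, so it is less precise than the raw QALY. The imbalance still carries over with the opposite sign: (−18 + 18ρ)/52 = −0.24 at ρ = 0.3 and −0.10 at ρ = 0.7.

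**The case against.** The strongest reply is that the plan is silent rather than wrong. It names no QALY estimator, so the unadjusted trapezium calculation is the reviewer's reading, and the whole QALY method is under-specified. That is fair as a description. But descriptive statistics are the only method named, so a raw difference is the natural default, and an undefined word cannot be credited as a covariate adjustment.

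It is also true that randomisation keeps the raw difference unbiased on average. Minimisation on physician-rated ECOG and treatment intent may reduce a utility imbalance, and SAP Table 1 would display it. Displaying an imbalance does not remove it from the ICER, however.

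Three stronger readings are tempting and are not supported:

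- *An ordinary imbalance could erase or reverse the result.* If the 0.5 SD effect is borrowed from the primary index and applied to utility at all three follow-up visits, the QALY difference is 0.5 × 0.2 × 18/52 = 0.035. Cancelling it needs a baseline gap of 0.035/0.219 = 0.158 at ρ = 0.3, 0.120 at ρ = 0.5 or 0.097 at ρ = 0.7. Those are 4.5, 3.4 and 2.7 SE, which is not ordinary. A smaller true effect would be easier to cancel, but the documents give none.
- *The trial loses power for the QALY comparison.* The plan makes no hypothesis test on QALYs, and its 0.5 SD relates to change in the primary index at 12 weeks.
- *The 38% SE cut at ρ = 0.5 is what to expect.* It assumes no deaths. Protocol 3.6.6 anticipates attrition from death in this population of patients aged 70 and over.

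**Conclusion.** The point holds as an omission with a better method available from data in hand. Under the stated assumptions, a baseline utility gap of 0.05 moves the 24-week QALY difference by about 0.011 to 0.018. Adjustment narrows the SE by 26% to 52% without deaths. At ρ = 0.5 the narrowing drops from 38% to about 13% to 24% if 10% to 20% die and score zero. Utility SD, correlation and mortality are all assumed, so these figures indicate scale and are not predictions.

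The issue is chance imbalance and lost precision, not bias. It concerns only the QALY difference and the ICER. The primary and secondary clinical conclusions do not depend on it. It is a free improvement of low priority, because the evaluation is exploratory.

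**What to change.** State in protocol 4.5.1 and in the SAP, before analysis:

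*Each participant's 24-week QALY will be the area under the utility curve, with utility zero after death. Incremental QALYs will be estimated by regressing this QALY on treatment arm and baseline utility from the same instrument. The adjusted arm difference will be the denominator of the ICER.*

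For QLU-C10D, add that the area uses the baseline, week 12 and week 24 visits. SAP Table 4 lists week 18 for this measure, but the QLQ-C30 is not scheduled then, so that entry should be reconciled. Define or delete the stray *adjusted* in the ICER sentence.

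The cost is a few sentences and one regression term. No new data are needed. A participant without a baseline utility would need a simple imputed value. Few should arise, since protocol 3.6.2 requires baseline assessment before randomisation. Fixing the rule now also removes a later choice between raw and adjusted ICERs.

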4.5.2. Interventions that result from integrated geriatric care

An exploratory objective of this study is to evaluate the interventions that result from integrated geriatric care. Data on medication prescribing patterns, recommendations made, referral patterns and adherence to recommendations will be collected on the study participants. Comparisons between treatment arms will be made where appropriate and the test selected depending on the distribution.

4.5.3. Relationship between components of HRQoL and CGA with clinical outcomes

An exploratory objective of this study is to assess which components of HRQoL and CGA predict clinical outcomes. The relationship between HRQoL and CGA components with survival, functional decline, chemotherapy delivery and healthcare utilisation will be evaluated. Specifically, the self-MNA, G8 screening tool, Flemish version of the Triage Risk Screening Tool (fTRST), CHSA clinical frailty scale, Adelaide Tool's assessment of frailty, Balducci criteria for frailty and the Cancer and Aging Research Group's model for predicting chemotherapy toxicity will be evaluated in terms of their ability to predict clinical outcomes.(14, 21, 28, 65, 75, 76)

4.5.4. Development of a brief geriatric assessment screening tool and predictive model for older adults with cancer

An exploratory objective of this study is to develop a brief geriatric assessment screening tool to detect health-related issues in older adults with cancer and to develop a predictive model to detect older adults with cancer who are at risk of poor clinical outcomes.

First, shorter versions of existing screening instruments will be compared against the full version. Specifically, the PHQ-4 will be compared against PHQ-9 and GAD-7 as a screening instrument for symptoms of depression and anxiety in the study population. PHQ-4 consist of the first two items of the PHQ-9 and GAD-7, and constitute the two core DSM-IV items for major depressive disorder and generalised anxiety disorder, respectively.(77, 78)

Next, in order to determine the effectiveness of different CGA components in screening for problems, comparisons will be made between different CGA components (e.g. 20-item problem checklist) and interventions that result from integrated geriatric care.

In addition, consideration will be given to developing a predictive model for clinical outcomes in older adults with cancer using a multivariate logistic regression model or cluster analysis.

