3.5. Study Intervention

3.5.1. Integrated Geriatric Care

Participants assigned to the intervention arm of the study will receive integrated geriatric care, in addition to standard oncology care (refer to **3.5.2**). Integrated geriatric care consists of a comprehensive geriatric assessment and management performed by the study doctor who is a consultant physician in the specialty of Geriatric Medicine. It has two essential components: the process of assessment coupled with an appropriate management plan.

The assessment should as a minimum cover:

- current active medical problems
- past medical history
- medication review
- immunisation status
- advanced care planning arrangements
- current and previous physical functioning
- psychological functioning including cognition and mood
- social function including living arrangements, financial arrangements, community services, social support and carer issues

The PRO measures collected at baseline assessment (except for the HRQoL questionnaires) and timed-up-and-go test (TUG) will form a component of the comprehensive geriatric assessment and will be available to the study doctor. Additional components of the comprehensive geriatric assessment will be collected using an additional self-reported questionnaire (refer to **Appendix 11**). This self-reported questionnaire is based on a modification of the Adelaide Tool(14) and the Cancer and Aging Research Group's predictive model for chemotherapy toxicity(21), and includes:

- Medical Outcome Survey (MOS) Core Survey items on general health, health change, ability to walk 1 block and social activity limitation because of physical/emotional health
- MOS Social Support Survey items on tangible support (4 of 4 items) and emotional social support (1 of 8 items),
- Older Americans Resources and Services (OARS) items on hearing and vision
- number of falls in the last 6 months
- Center for Epidemiologic Studies Depression scale (CES-D) items on exhaustion
- pain numerical rating scale
- Distress Thermometer and Canadian Problem Checklist (20 of 21 items; one item on practical problems related to work/school was not included because it was thought not relevant to the study population's age-group)

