The remainder of the assessment and development of the management plan must include a personal attendance by the study doctor. This attendance should include performance-based assessment of cognition by Montreal Cognitive Assessment (MoCA). A prioritised list of diagnoses/problems will be developed based on the information derived from the history and examination, and any additional information provided by other means, including an interview of a person other than the patient.

The management plan will be individualised to the patient's needs and may include:

- measures to optimise concurrent health issues
- medication recommendations
- non-medication recommendations (e.g. lifestyle changes, including exercise and diet)
- assessment of the risk of chemotherapy toxicity
- referrals to relevant existing hospital and community services (e.g. allied health services, rehabilitation services, aged care services, palliative care services)

The management plan should be explained and, if necessary, provided in written form to the patient or, where appropriate, their family or carer(s). A written report of the comprehensive geriatric assessment and management plan will be communicated back to the treating oncologist and general practitioner within a maximum of 2 weeks of the assessment via email or mail. More prompt verbal communication may be appropriate.

Participants assigned to the intervention arm will receive a comprehensive geriatric assessment and management within 3 weeks of randomisation. Participants assigned to the intervention arm will continue to see their oncologists who are the participants' primary physician for treatment of their cancer and related health conditions. Further reviews with the study doctor will occur at approximately 12 weeks and 24 weeks after randomisation. The 12 weeks and 24 weeks reviews should include performance-based assessment of functional mobility by TUG. Additional reviews with the study doctor may be scheduled as required depending on medical needs.

Assessments of outcome measures occur at 12 weeks, 18 weeks and 24 weeks following randomisation. After 24 weeks, participants in the intervention arm may continue to receive integrated geriatric care but will not be required to complete further study assessments.

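### Protocol 4.5.4 judges CGA components as screening tools against interventions chosen by the doctor whose assessment contains them, so the comparison can show yield but not screening effectiveness

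*Combined protocol and SAP*

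**What the plan says.** Protocol 4.5.4 sets the goal: "An exploratory objective of this study is to develop a brief geriatric assessment screening tool to detect health-related issues in older adults with cancer". One step, taken "in order to determine the effectiveness of different CGA components in screening for problems", is a comparison of components with what was done: "comparisons will be made between different CGA components (e.g. 20-item problem checklist) and interventions that result from integrated geriatric care".

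Protocol 3.5.1 says where those interventions come from. Integrated geriatric care is a "comprehensive geriatric assessment and management performed by the study doctor who is a consultant physician in the specialty of Geriatric Medicine". The baseline patient-reported measures (apart from the HRQoL questionnaires) and the TUG "will form a component of the comprehensive geriatric assessment and will be available to the study doctor". The same section states that "Additional components of the comprehensive geriatric assessment will be collected using an additional self-reported questionnaire", and lists within that questionnaire the "Distress Thermometer and Canadian Problem Checklist (20 of 21 items". The doctor then works towards a plan: "A prioritised list of diagnoses/problems will be developed based on the information derived from the history and examination", together with information from other sources. SAP 2.4.1 repeats this description.

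SAP 1.2 lists the screening-tool objective. The SAP text supplied gives no method for it: no reference standard, no blinded adjudication and no caveat.

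**The concern.** To judge how well a component screens for problems, one needs a view of who has the problem that was formed without that component. Here the yardstick is the set of actions taken by a doctor who holds the component while deciding on them. Two errors follow.

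- **The test feeds the reference (incorporation bias).** A tick that prompts a referral counts as a correct detection whether or not a problem existed.
- **The reference measures something else.** A real problem for which no intervention is available or accepted counts as no problem, and an intervention given without a problem counts as one.

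At stake is what the trial may say about which components work as screening tools. A larger sample would not help, because the fault lies in the reference and not in precision.

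**Working it through.** **What the documents supply.** They give the index test (CGA components, with the 20-item checklist as the example), the reference (resulting interventions), and one doctor for both assessment and plan. Access to the components is explicit for the baseline patient-reported measures and the TUG. For the checklist it is an inference, though a strong one, because the questionnaire holding it is collected as part of the assessment this doctor performs. The HRQoL questionnaires are withheld, so this route does not reach them.

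**The plan's own figure.** None is stated for this analysis. The only usable number is the size of the intervention arm, 64 evaluable. That reproduces from the primary sample-size inputs (effect size 0.5, two-sided 0.05, 80% power): an exact two-sample t-test calculation gives 64 per group with power 0.801.

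**Assumptions (not in the documents).** Prevalence of the problem is 0.30. Without the item, the doctor intervenes with probability d = 0.80 if the problem is present and d = 0.05 if it is absent. A tick alone adds a chance q of intervention, so

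P(intervention | tick) = 1 - (1 - d)(1 - q).

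**Item ticked at random in 30% of participants (true ratio 1.0).**

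- Unticked: 0.30 × 0.80 + 0.70 × 0.05 = 0.275.
- Ticked, q = 0.25: 0.30 × 0.85 + 0.70 × 0.2875 = 0.456, a ratio of 1.7.
- Ticked, q = 0.50: 0.30 × 0.90 + 0.70 × 0.525 = 0.638, a ratio of 2.3.
- Apparent sensitivity, q = 0.25: 0.30 × 0.456 / (0.30 × 0.456 + 0.70 × 0.275) = 42%. At q = 0.50 it is 50%. The truth is 30%.
- Apparent specificity is 76% and 82%. The truth is 70%.

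**Good item (sensitivity 80%, specificity 90%), q = 0.25.**

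- Ticked: 0.24 with the problem and 0.07 without. Unticked: 0.06 and 0.63.
- Ticked and intervened: 0.24 × 0.85 + 0.07 × 0.2875 = 0.2241.
- Unticked and intervened: 0.06 × 0.80 + 0.63 × 0.05 = 0.0795.
- Apparent sensitivity: 0.2241 / (0.2241 + 0.0795) = 74%, against 80%.
- Apparent positive predictive value (PPV): 0.2241 / 0.31 = 72%, against a true 0.24 / 0.31 = 77%.

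**Moderate item (sensitivity 60%, specificity 80%, true PPV 0.18 / 0.32 = 56%), by the same steps.**

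| q | Apparent sensitivity | Apparent specificity | Apparent PPV |
|---|---|---|---|
| 0.10 | 58% | 79% | 52% |
| 0.25 | 61% | 81% | 60% |
| 0.50 | 66% | 87% | 74% |

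The PPV moves from understated to overstated at q of about 0.17.

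**Detectability with 64 participants.** This is a separate illustration for an uninformative item. Let b be the probability of intervention without the item (0.2-0.5), w the added reliance on a tick, and item prevalence 0.2-0.5. Then P(intervention | tick) = b + (1 - b)w. With b = 0.2 and w = 0.25 this is 0.40, and the odds ratio is (0.40/0.60) / (0.20/0.80) = 2.67. In simulation (1,500 runs per setting), Fisher's test gave p < 0.05 in about 3-4% of runs at w = 0, 4-9% at w = 0.10, 9-35% at w = 0.25 and 31-90% at w = 0.50.

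**The case against.** The best reply has four parts.

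- **Direction.** A reader might infer that screening performance is overstated by construction. The figures above do not support that: an error-prone yardstick pulls against the circularity, and at low reliance, or for a good item, the net effect is understatement. This part stands.
- **Certainty.** A reader might infer that a useless item is bound to look effective. It does so only if the doctor acts on it. Section 3.5.1 requires personal attendance, history and examination, and an item the doctor ignores would show no association. This part also stands: "can" is supportable, "will" is not.
- **Consequence.** A reader might infer that items will be kept in the brief tool because they were acted on. Section 4.5.4 states no retention rule and names no accuracy measure. It also plans a comparison of the PHQ-4 with the longer scales and considers outcome modelling, so this comparison is not the only input. That outcome is possible but not planned in the text.
- **Natural reading.** Comparing components with interventions can be read as yield. The comparison alone can; the aim attached to it, effectiveness in screening for problems, cannot. This part does not answer the point.

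Exploratory status limits the consequence but does not make the reference independent.

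**Conclusion.** The point holds in a limited form. As written, the comparison in 4.5.4 cannot answer its stated aim, because the reference is partly produced by the tests being judged and because intervention is not the same construct as problem. An uninformative item can look effective, and a good one can look worse than it is. Direction and size depend on the item and on the doctor's reliance on it, which the documents do not give.

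The 46-64% against 28%, and the 74% and 72% for the good item, rest on the assumed prevalence, intervention probabilities and q. They illustrate the mechanism and do not predict the trial's result. Access to the checklist itself is inferred. Only one exploratory objective is touched; nothing here bears on the primary or secondary analyses.

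**What to change.** In protocol 4.5.4, and in a short method paragraph added to the SAP:

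1. Report this comparison only as yield: in the intervention arm, how often a positive component was followed by a related recommendation or referral. Draw no conclusion from it about screening effectiveness or about which items to keep.
2. Claim screening accuracy only against a reference set without sight of the component under test, such as a measure already collected that does not contain that component. Where none exists, make no accuracy claim.

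Substituting the doctor's prioritised problem list as the reference would mostly move the circularity. The same doctor makes it from the same information, a tick may prompt the history that then supports the problem, and the documents do not say that the report records the source of each problem.

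The cost is a change of wording and a narrower exploratory conclusion. The yield analysis uses the recommendation and referral data that protocol 4.5.2 already collects, so no new data are needed.
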